**Study Design:**

This is a randomized, double-blind, vehicle-controlled, multicenter, parallel-group study in adult subjects with clinically-confirmed mild to moderate AKs on the face and the balding scalp, to be conducted at approximately 60 clinical sites in the United States. Sites will be selected to ensure that diverse daylight conditions will be represented in the study to understand the effects of latitude, elevation, and climate.

After a screening visit, approximately 570 subjects will be randomized in a 2:1 ratio to receive 2 treatments of daylight photodynamic therapy (DL-PDT) with either MAL cream 16.8% (CD06809-41) or a vehicle cream. The 2 treatments will occur at least 2 weeks up to 4 weeks apart, Visit 2 (first DL-PDT) and Visit 4 (second DL-PDT). Other study visits will occur 1 week after each of the PDT treatments (Visits 3 and 5) for safety assessments and 12 weeks after the last PDT treatment (Visit 6) for efficacy and safety assessments.

A subject will be considered to have a CR if all AK lesions treated with the study drug and then illuminated by daylight PDT are clear at Visit 6 (Final Visit).

Those subjects who have a CR at Visit 6 will be followed in the long-term follow-up study for recurrence of the treated AKs.

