**Table 4: Prior treatments**

| Treatment(s)  | Timeframe* |
|--|-------------------|
| Topical : 5-fluorouracil, diclofenac, imiquimod, retinoids, alpha-hydroxy acid, salicylic acid ointment, ingenol mebutate                              | 12 weeks          |
| Surgical: elliptical excision, excision and reconstructive surgery, Mohs' micrographic surgery, chemical peels/chemosurgery, cryosurgery, dermabrasion | 12 weeks          |
| Photodynamic therapy   | 12 weeks          |

|   |          |
|---|----------|
| Laser therapy   | 12 weeks |
| Electrocoagulation therapy  | 12 weeks |
| Radiotherapy  | 12 weeks |
| Investigative therapies for actinic keratosis   | 12 weeks |
| Systemic retinoids  | 12 weeks |
| Immunosuppressive agents such as glucocorticoids, cytostatic agents, antibodies, drugs acting on immunophilins, interferon, TNF binding proteins, mycophenolate mofetil, or biologics | 12 weeks |

\*minimum washout period prior to baseline

10. Planned or expected major surgical procedure during the clinical study
11. Currently participating or participated in any other study of a drug or device, within the past 12 weeks before the screening visit, or is in an exclusion period (if verifiable) from a previous study
12. Subjects with any condition that may be associated with a risk of poor protocol compliance
13. Any medical or psychological condition or any clinically relevant laboratory abnormalities, such as but not limited to elevated ALT or AST ( $> 3 \times \text{ULN}$ ) in combination with elevated bilirubin ( $> 2 \times \text{ULN}$ ), at the screening or baseline visit that may put the subject at significant risk according to the investigator's judgment, if he/she participates in the clinical study, or may interfere with study assessments (e.g., poor venous access or needle-phobia).
14. Subjects unwilling to refrain from using prohibited medications during the clinical study (see [Section 8.4.7](#))

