### 8.3.4 Removal of Subjects From Therapy or Assessments

Although the importance of completing the entire clinical study will be explained to the subjects, any subject is free to discontinue his/her participation in the study at any time and for whatever reason, specified or unspecified, and without any prejudice. No constraints are to be imposed on the subject, and when appropriate, a subject may be treated with other conventional therapy when clinically indicated. Investigators or the Sponsor can also withdraw subjects from the clinical study if deemed to be necessary. Data collected up to the time of subject removal will be used.

Reasons for discontinuing study drug include:

- WITHDRAWAL BY SUBJECT  
Subject request (i.e., consent withdrawal)
- PROTOCOL VIOLATION  
Use of non-permitted concurrent therapy (unless discussed and agreed upon with the Investigator and medical monitor)
- NON-COMPLIANCE WITH STUDY DRUG

---

Non-compliance with the study drug or study schedule

- LOST TO FOLLOW-UP
- ADVERSE EVENT

Occurrence of AEs not compatible with the continuation of subject participation in the study, in the Investigator's opinion, or unacceptable to the subject to continue, such as serious immediate-type allergic manifestations, including anaphylactic reaction.

- PREGNANCY
- PHYSICIAN DECISION
- LACK OF EFFICACY
- OTHER
- INTERCURRENT ILLNESS
  - Diagnosis of a malignancy (except curatively treated *in situ* cervical carcinoma or BCC in areas outside of treatment areas studied in this protocol)
  - Any opportunistic infection (such as active TB and other infections whose nature or course suggest an immune-compromised status)

The reason(s) for withdrawal will be documented in the eCRF. Subjects who have been enrolled and treated will not be replaced by another subject.

Subjects who prematurely discontinue study drug will be encouraged to complete the scheduled study visits.

When a subject discontinues study drug, he/she will be fully assessed whenever possible, and followed according to guidelines presented in [Section 8.5.1](#) (Early Termination Visit).

Reasonable efforts will be made to contact subjects who are lost to follow-up. These efforts must be documented in the subject's file.

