#### 8.4.7 Prior and Concomitant Therapy

Prior therapies are defined as therapies that have been stopped within the 3 months before the screening visit, unless relevant to the inclusion/exclusion criteria. Whenever possible, prior therapies for AK should be documented.

Concomitant therapies/medications are defined as follows:

- Any existing therapies ongoing at the time of the screening visit,
- Any changes to existing therapies (such as changes in dose, formulation, or application frequency) during the course of the study, or
- Any new therapies received by the subject since the screening visit

The following 2 categories are to be considered for prior and concomitant therapies:

- Drugs/Therapies include but are not limited to prescription, over-the-counter, birth control pills/patches/hormonal devices, vitamins, moisturizers, sunscreens, herbal medicines/supplements, and homeopathic preparations.
- Medical and surgical procedures (e.g., phototherapy, exodontia). Procedures whose sole purpose is diagnosis (non-therapeutic) are not included.

Prior and concomitant therapies for drugs/therapies or for medical/surgical procedures are to be recorded in the appropriate eCRF.

Concomitant therapies are to be recorded, reviewed, and updated at each visit.

At each visit, Investigators should also confirm concomitant therapies for contraception. Contraceptive counseling should occur at Screening.

Any new concomitant therapy or modification of an existing therapy may be linked to an AE. In such cases, a corresponding AE form should be completed to account for the new therapy or change in therapy, in which case the medication will be linked to an item in the subject's medical history.

The therapies listed in [Table 4](#) are also considered prohibited because they may interfere with the

---

efficacy and/or safety assessments of the study drug.

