In addition, administration of analgics (including anti-inflammatory and corticosteroids at doses that relieve pain) should be avoided from the day preceding the treatment procedure until the subject self-assessment of pain is completed, in order for subjects to not underestimate any pain that may be experienced. For the same reason, use of local treatment on treatment areas such as xylocaine spray, nerve blocks, and cooling procedures (such as cold-water spray or a cooling fan) are not allowed before and during the treatment procedures until the subject's self-assessment of pain is completed. Cooling procedure may be used after the subject's self-assessment of pain is completed, if this is current practice at the site.

In case the subject is using topical therapy listed in [Table 4](#) or treatment listed above on other area than TAs, the Investigator will remind him/her to pay strict attention to not apply any of these therapies on the TA.

If prohibited therapies become a necessary treatment for the safety or best interest of the subject, the medical monitor should be notified to discuss possible alternatives prior to administration of a prohibited therapy.

If a subject receives prohibited therapy during the clinical study, the medical monitor should be notified to discuss the pertinence and the modalities to be used for the subject to continue in the clinical study.

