6 EFFICACY AND SAFETY VARIABLES

6.1 Efficacy Variables

6.1.1 Lesion Response

At Visit 2 (before treatment), the Investigator will map the subject's lesions, count them, and report their severity according to criteria based on Olsen (1991) (see Table 2).

At Visits 2b (if applicable), 4, 4b (if applicable) before treatment and at Visit 6/ET, the severity of pre-existing, treated AK lesions that had been identified and treated previously will be recorded. If new AKs develop in the treatment area, they will be recorded, but not treated nor included into the efficacy evaluations.

Table 2 - Lesion Severity Grade Scale

Grade	Severity	Description
Grade 1	Mild	Slightly palpable, better felt than seen
Grade 2	Moderate	Moderately thick, easily felt and seen
Grade 3	Severe	Very thick and/or obvious actinic keratoses

The Investigator will be asked at Visits 2b (if applicable), 4, 4b (if applicable) and 5/ET to identify each lesion treated previously, and the lesion response as a CR or a non-CR, as described in Table 3.

Table 3 - Lesion Response Score

Response	Score	Description
Complete response (CR)	1	Complete disappearance of the lesion, visually and by palpation
Non-complete response (non-CR)	0	Non-complete disappearance of the lesion

If all of the treated lesions in the treatment area are assessed to be CR at 12 weeks after the last DL-PDT session (Visit 6), the subject will be assessed as a subject CR. If any of the treated lesions in the treatment area are assessed to be non-CR, the subject will be assessed as a non-complete responder. Those subjects who are assessed to be CR, i.e., all treated lesions cleared, at Visit 6 will be offered the opportunity to continue in the long-term follow-up study, to assess recurrence of lesions treated.

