10.6.1 Analysis of the Primary Endpoint

The hypothesis test for the primary endpoint can be formally defined as follows:

$$\begin{cases} H_0: \Pi_{MAL} = \Pi_{Vehicle} \\ H_a: \Pi_{MAL} \neq \Pi_{Vehicle} \end{cases}$$

where Π_{MAL} is the proportion of subjects achieving a complete response at 12 weeks after the last MAL DL-PDT and $\Pi_{Vehicle}$ is the proportion of subjects achieving a complete response at 12 weeks after the last vehicle DL-PDT.

The hypothesis test for the primary endpoint will be evaluated on the ITT population at the two-sided significance level $\alpha = 0.00125$. Efficacy will be claimed if the between treatment difference on the primary endpoint is statistically significant with a p-value < 0.00125 . This result will provide an acceptable level of evidence of efficacy, in presence of good internal consistency across primary and secondary endpoints in the absence of a second pivotal study.

The proportion of subjects with complete clearance of all AK lesions treated at each post-baseline analysis visit will be summarized descriptively by treatment groups (overall and by analysis centers). The proportion of subjects with complete clearance of all AK lesions treated at 12 weeks after the last DL-PDT (Visit 6) will be analyzed using the Cochran-Mantel-Haenszel (CMH) test stratified by analysis center (see definition in section 10.6.4.4). No continuity correction will be used. The p-value for the treatment comparison (MAL DL-PDT vs. vehicle DL-PDT) will be calculated from the general association statistic of the stratified CMH test. Difference in proportions between treatment groups and the 99.875% and 95% confidence intervals of the difference will be based on the large sample approximation method for binary data and will be calculated using the method described in the Huiping Zhang "Proportion difference and confidence interval based on Cochran-Mantel-Haenszel method in stratified multi-center clinical trial", 2016, PharmaSUG China 2016, Paper 25 [1]. In addition, the proportion of subjects with complete clearance of all AK lesions treated at 12 weeks after the last DL-PDT (Visit 6) for each treatment group will also be presented.

For the primary analysis, all subjects on the ITT population with missing data for the primary endpoint will be classified as non-responders regardless of treatment allocation (see section 10.6.4.2).

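### A study-treated lesion cleared by a prohibited AK therapy before Visit 6 can count as a study-treatment success in the ITT primary and secondary analyses, because only missing data have a scoring rule

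*SAP*

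**What the plan says.** **Response.** SAP 6.1.1 (Table 3) and Protocol 9.1.1 (Table 7) define lesion complete response as "Complete disappearance of the lesion, visually and by palpation", scored 1, with everything else scored 0. There is no category for a lesion treated by other means. The synopsis counts a subject as a complete responder "if all AK lesions treated with the study drug and then illuminated by daylight PDT are clear at Visit 6".

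**Non-response by rule.** For the primary endpoint, SAP 10.6.1 states that "all subjects on the ITT population with missing data for the primary endpoint will be classified as non-responders regardless of treatment allocation". SAP 10.6.3 applies the same rule to partial response (75% or greater reduction). For percent reduction, missing counts are multiply imputed under MAR. SAP 10.6.4.2 adds no rule for any event other than missing data.

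**Other AK therapy.** Protocol Table 4 lists local treatments that include "chemical peels/chemosurgery, cryosurgery, dermabrasion", excision, Mohs surgery, laser, photodynamic therapy, 5-fluorouracil and imiquimod. Protocol 8.4.7 says that the Table 4 therapies "are also considered prohibited because they may interfere with the" assessment of efficacy or safety. If a subject nevertheless receives one, the medical monitor is contacted "to discuss the pertinence and the modalities to be used for the subject to continue in the clinical study". Protocol 8.3.4 adds: "Subjects who prematurely discontinue study drug will be encouraged to complete the scheduled study visits".

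**Consequence in the analysis.** Use of prohibited therapy is a potential major deviation (Protocol 10.3, SAP 8.3) that can exclude the subject from the per-protocol (PP) population. The PP analysis is planned for the primary endpoint only.

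**The concern.** The endpoint is meant to show clearance by MAL with daylight. The protocol itself regards the Table 4 therapies as interfering, yet the scoring rule cannot tell a lesion cleared by study treatment from one that was frozen or excised during the 12-week wait. Following the plan as written, the second lesion is a success.

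Three quantities could be affected: the complete response rate in each arm, the difference between arms, and both secondary endpoints, which are tested in sequence at the same 0.00125 level. The trial is intended to stand without a second pivotal study and on consistency between primary and secondary endpoints. What counts as a response should therefore be fixed in advance.

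**Working it through.** **1. Does the plan's text lead to this scoring?**

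- A subject withdrawn before Visit 6 has no Week 14 value, because SAP 10.6.4.9 (Table 9) keeps early termination as a separate analysis visit. That subject is already a non-responder for complete and partial response. The gap does not concern these subjects.
- A subject who stays has an observed Visit 6 value, so the missing-data rule does not apply. Lesion status is read as present or gone.
- Protocol 8.3.4 lists non-permitted therapy as a reason to stop study drug. Once the second session is complete there is no study drug left to stop, so this does not make Visit 6 missing.
- The sensitivity analyses in SAP 10.6.2 address missing data, the PP population, COVID-19 disruption and one unverifiable site. None rescores lesions that received other therapy.

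**2. What does one such lesion change?** For complete response it matters only if every remaining treated lesion ends clear. For percent reduction with *n* treated lesions, each one moves the subject by 100/*n* points: 100/4 = 25 at the minimum of 4 lesions and 100/12 = 8.3 at the maximum of 12. For partial response, a subject with 5 of 8 cleared (62.5%) reaches 6 of 8 (75%) and becomes a responder.

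**3. The plan's own figures.** Inputs from SAP 9 and 10.1.5: 380 MAL and 190 vehicle subjects, 45% v 15%, two-sided alpha 0.00125 (z = 3.227), 7% non-evaluable. The unstratified normal approximation is

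power = Φ[(p₁ − p₂ − z·s₀)/s₁], with s₀ = √(p̄(1−p̄)(1/n₁+1/n₂)) and s₁ = √(p₁(1−p₁)/n₁ + p₂(1−p₂)/n₂).

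At 45% v 15%, s₀ = 0.0424 and s₁ = 0.0364, so power exceeds 99.99%. The stated figure of more than 90% is met. With 7% missing scored as failures, the expected rates are 0.93 × 45% = 41.85% and 0.93 × 15% = 13.95%. The difference is 27.9 points and power still exceeds 99.9%.

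**4. Size, on assumed rates.** Let *r* be the share of evaluable would-be non-responders who are scored as complete responders after other therapy. The documents give no value for *r*.

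- MAL rate = 0.93 × (0.45 + 0.55·r_MAL)
- Vehicle rate = 0.93 × (0.15 + 0.85·r_veh)

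| r MAL | r vehicle | MAL | Vehicle | Difference (points) | Power |
|---|---|---|---|---|---|
| 0 | 0 | 41.9% | 14.0% | 27.9 | >99.9% |
| 2% | 2% | 42.9% | 15.5% | 27.3 | >99.9% |
| 5% | 5% | 44.4% | 17.9% | 26.5 | >99.9% |
| 10% | 10% | 47.0% | 21.9% | 25.1 | 99.8% |
| 0 | 5% | 41.9% | 17.9% | 23.9 | 99.7% |
| 0 | 10% | 41.9% | 21.9% | 20.0 | 94.6% |
| 0 | 20% | 41.9% | 29.8% | 12.1 | 33% |
| 5% | 0 | 44.4% | 14.0% | 30.5 | >99.9% |
| 10% | 0 | 47.0% | 14.0% | 33.0 | >99.9% |

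Example, vehicle only at 10%: 0.93 × (0.15 + 0.085) = 0.2186, and 0.4185 − 0.2186 = 0.200. That is 190 × 0.93 × 0.85 × 0.10 = 15 extra vehicle responders, or 0.0791/0.2186 = 36% of all vehicle responses.

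**5. The other direction.** Suppose there is no true effect (15% in both arms) and other therapy clears lesions on MAL only. The chance of a significant result favouring MAL rises from 0.0006 to 0.0028 (r = 2%), 0.018 (5%) or 0.15 (10%). Nothing in the documents makes this pattern likely. It shows only that the unstated rule is not conservative in every case.

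**The case against.** Much of the case for leaving the plan alone is sound.

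- **The route is narrow.** The therapies are prohibited, the medical monitor is to be told before one is given, and users of listed topicals elsewhere are reminded to keep them off the treatment area. Protocol 8.4.7 permits continuation; it does not say that users are kept in. This stands, and it limits the point to violators who stay to Visit 6.
- **Part of it is handled.** The primary analysis is repeated on the PP population, and the blind review may exclude subjects or data before lock. This stands in part. PP exclusion drops the subject rather than counting a failure, no PP analysis covers the secondary endpoints, and the blind review has no stated criterion for this event.
- **The likely bias is conservative.** Lesions persist more often on vehicle, so other therapy is probably commoner there. This stands as an expectation; the documents offer no data. Scoring observed status regardless of other therapy is also a recognised ITT choice, but neither document states that choice, and Protocol 8.4.7 treats these therapies as interfering.

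A reader might infer three stronger things that the documents do not support:

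- **That the protocol freely allows other AK treatment on study.** The statement in Protocol 8.3.4 that "when appropriate, a subject may be treated with other conventional therapy when clinically indicated" follows directly on the subject's freedom to leave. It reads mainly as describing subjects who discontinue, and those without a Visit 6 value are already non-responders.
- **That the primary conclusion is in danger.** At the design rates, power stays near 95% even with 10% contamination on vehicle alone.
- **That the long-term follow-up cohort would be put right by the same change.** The offer rests on the investigator's Visit 6 assessment, which an analysis rule does not alter, and that study's own criteria are not in these documents.

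**Conclusion.** The gap is real but limited. As written, the ITT primary and both secondary analyses can count a study-treated lesion cleared by a prohibited Table 4 therapy as a success. It affects only subjects who receive such therapy on a study-treated lesion and are seen at Visit 6. Their number is unknown, and every contamination rate above is an assumption.

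If use is balanced at 2% to 10% of would-be non-responders, the difference falls by about 0.6 to 2.8 points (27.9 to 27.3 or 25.1) and both response rates are too high. If use is on vehicle only at 5% to 10%, the difference falls by about 4 to 8 points (27.9 to 23.9 or 20.0). In these cases a reversal of the primary test is unlikely at the design rates. The main effect is on the size of the estimate and on what a complete response means. The secondary endpoints are more exposed, since a single lesion can change them and no PP analysis covers them. The rule is worth settling before database lock.

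**What to change.** Add the following to SAP 10.6.1, 10.6.3 and 10.6.4.2:

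- A subject with a local AK therapy or procedure from Protocol Table 4 recorded on a study-treated lesion between the first DL-PDT and Visit 6 is a non-responder for complete response.
- For percent reduction and partial response, the affected lesion counts as not cleared. If the record does not identify the lesion, all study-treated lesions in the recorded area count as not cleared.
- As-observed scoring of all three endpoints is kept as a sensitivity analysis.

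This concerns scoring only and changes nothing in how subjects are managed. The systemic agents in Table 4 are outside the rule and would remain with the PP exclusion.

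**Cost.** Response rates become slightly lower. Therapies and procedures are already recorded in the eCRF (Protocol 8.4.7), but neither document says that they are linked to mapped lesions. A blinded review of those records for location is therefore needed before lock, and the area-level fallback covers records that cannot be resolved.

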10.6.2 Sensitivity Analyses of Primary Endpoint

To assess the robustness of the primary efficacy results, the following sensitivity analyses will be conducted:

Statistical Analysis Plan

1. The primary analysis will be repeated on the ITT population by imputing missing data using MI (Multiple Imputation) under the Missing At Random (MAR) assumption (see section 10.6.4.2 for further details).
2. The primary analysis will be repeated on the ITT population by imputing missing data using MI (Multiple Imputation) based on the Pattern-Mixture Model under the missing not at random (MNAR) assumption, by using the profiles from vehicle DL-PDT subjects with observed data to impute missing data (see section 10.6.4.2 for further details).
3. The primary analysis will be repeated on the ITT population by imputing missing data using MI (Multiple Imputation) based on the Pattern-Mixture Model under the missing not at random (MNAR) assumption in order to perform a tipping-point analysis (see section 10.6.4.2 for further details).
4. The primary analysis will be repeated on the ITT population by imputing missing data using Last Observation Carried Forward (LOCF).
5. Observed Case (OC) analysis on the ITT population.
6. The primary analysis will be repeated on the PP population.

